# 7.7 Premature termination of the study

As botulinum toxin is an established and safe therapy for other indications (see also section on safety), Functional magnetic resonance imaging is a non-invasive and safe procedure and is very commonly used in clinical practice and research. An interim analysis is not considered necessary

## **8. SAFETY REPORTING**

## 8.1 Section 10 WMO event

In accordance to section 10, subsection 4, of the WMO, the sponsor will suspend the study if there is sufficient ground that continuation of the study will jeopardise subject health or safety. The sponsor will notify the accredited METC without undue delay of a temporary halt including the reason for such an action. The study will be suspended pending a further positive decision by the accredited METC. The investigator will take care that all subjects are kept informed.

## 8.2 Adverse and serious adverse events

Adverse events are defined as any undesirable experience occurring to a subject during the study, whether or not considered related to the investigational drug or the experimental treatment. All adverse events reported spontaneously by the subject or observed by the investigator or his staff will be recorded.

A serious adverse event is any untoward medical occurrence or effect that at any dose:

- results in death;
- is life threatening (at the time of the event);
- requires hospitalisation or prolongation of existing inpatients' hospitalisation;
- results in persistent or significant disability or incapacity;
- is a congenital anomaly or birth defect;
- is a new event of the trial likely to affect the safety of the subjects, such as an unexpected outcome of an adverse reaction, lack of efficacy of an IMP used for the treatment of a life threatening disease, major safety finding from a newly completed animal study, etc.

All SAEs will be reported through the web portal ToetsingOnline to the accredited METC that approved the protocol, within 15 days after the sponsor has first knowledge of the serious adverse reactions.

SAEs that result in death or are life threatening should be reported expedited. The expedited reporting will occur not later than 7 days after the responsible investigator has first knowledge of the adverse reaction. This is for a preliminary report with another 8 days for completion of the report.

A predefined list of AE's will be reported periodically instead of individually using the CCMO-module 'toetsingOnline'. AE's that will be listed and reported periodically are the following:

local pain

- flu symptoms
- muscle weakness
- local haematomas

## 8.2.1 Suspected unexpected serious adverse reactions (SUSAR)

Adverse reactions are all untoward and unintended responses to the investigational product related to any dose administrated. Unexpected adverse reactions are adverse reactions, of which nature, or severity, is not consistent with the applicable product information i.e. the summary of the product characteristics.

Using CCMO module 'Toetsing Online' all SUSAR's that could have consequences for the safety of the subjects involved in trial will be reported to the CCMO and central METC. The reporting will occur within 15 days after the investigator has first received information on the SAE. For fatal or life-threatening cases a preliminary report will be offered within 7 days followed by a complete report within 8 days.

The remaining SUSAR's are recorded in a overview list(line listing) that will be submitted once every 6 months to the METC. This line listing provides an overview of all SUSAR's concerning the trial medication, accompanied by a brief report highlighting the main points of concern.

## 8.2.2 Annual safety report

In addition to the expedited reporting of SUSARs, the investigator will submit, once a year throughout the clinical trial, a safety report to the accredited METC, competent authority, Medicine Evaluation Board and competent authorities of the concerned Member States. This safety report consists of:

- a list of all suspected (unexpected or expected) serious adverse reactions, along with an aggregated summary table of all reported serious adverse reactions, ordered by organ system, per study;
- a report concerning the safety of the subjects, consisting of a complete safety analysis and an evaluation of the balance between the efficacy and the harmfulness of the medicine under investigation.

## 8.2.3 Follow-up of adverse events

All adverse events will be followed until they have abated, or until a stable situation has been reached. Depending on the event, follow up may require additional tests or medical procedures as indicated, and/or referral to the general physician or a medical specialist.

# 8.3 Data Safety Monitoring Board

This study is considered a low risk trial. It is therefore decided not to institute a Data Safety Monitoring Board. An independent monitor from the CRU will monitor the data. In all trial subjects the informed consent forms and the in- and exclusion criteria will be checked. Source data verification will be performed in a sample of the population. The monitor also verifies whether all SAE's and SUSAR's are appropriately reported within the time frames required by GCP, the protocol, the ethics committee, and the applicable regulatory requirement(s).

## 9. STATISTICAL ANALYSIS

## 9.1 Descriptive statistics

Patient and clinical baseline characteristics will be summarized using simple descriptive statistics. Baseline values will consist of both categorical (e.g. sex, type of jerks, type of psychiatric conditions) and continuous variables (e.g. age, scores on questionnaires concerning neurological or psychiatric symptoms).

## 9.2 Univariate analysis

An intention to treat analysis will be performed with regard to the trial results. The difference in the proportions of patients reaching the primary outcome measure between the groups treated with BoNT and with placebo will be assessed using the  $\chi 2$  statistic or Fisher's exact test, when appropriate. For the secondary outcome measures, proportional differences between the groups will be tested with the  $\chi 2$  statistic. Difference in continuous secondary outcome measures will be assessed with the Students t-test or ANCOVA. For the long term effects, the assessments of individual patients at t=16 months will be compared with previous assessments using tests for paired data (paired t-test, McNemar's symmetry  $\chi 2$  test for paired responses) or the mean difference between T = 16 months and T = 0. Finally, we will analyse repeated measures data using mixed effects models. In all analyses statistical uncertainties will be expressed in 95% confidence intervals.

Concerning the fMRI study the main study outcome measure is the difference in BOLD signal between scans of patients with psychogenic jerks before and after treatment with BoNT. Secondary outcome will be patterns of representations of external space and body scheme in patients compared to the patterns seen in healthy subjects. Another secondary outcome will be the performance of patients in the self-referenced and target-based finger movement task itself.

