# Study population

A total of 54 patients with one or more jerks of psychogenic origin will be included in the study. To be included, patients need to experience to be significantly impaired in daily functioning due to at least one specific jerk. For the trial phase of the study, patients will be randomized in a 1:1 ratio to treatment with BoNT or to treatment with placebo. After 16 weeks, when the trial phase of the study is over, all patients will be included in the study on the long-term effect of treatment. Patients with serious complications during the trial period will not be included in second part of the study. For our fMRI sub-study approximately 16 patients of our total study population will be included. They will be compared to 16 neurologically and psychiatrically healthy volunteers.

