## 4.4 Sample size calculation

No prior results are available to clearly base the sample size calculation on. Hence, we chose to base our calculation on an expected difference in proportions reaching the primary endpoint between treatment with BoNT and placebo. For the expected proportions, we took the results of two prior trials studying the effect of BoNT into account. First, a trial in writer's cramp showed an effect in 32% of patients allocated to placebo and in 70% of patients allocated to BoNT on a patient rated primary endpoint. 11 Second, a cross-over trial in patients with motor tics showed no change in tics per minute in patients treated with placebo. Patients with tics and dystonia often have concurrent psychiatric disease as well. 12, 13 As the placebo effect may be large in patients with psychogenic disorders,  we expect that approximately one third of patients allocated to placebo treatment and approximately two thirds of patients allocated to BoNT may reach the primary endpoint. A two group Chi-square test with a 0,05 two-sided significance level will have 80% power to detect the difference between a control group proportion of 0,30 and a treatment group proportion of 0,70 (odds ratio of 5,4) when the sample size in each group is 24. As the side effects of therapy are mild and self-limiting and because only two injections are given in the trial period, we expect practically no withdrawals in this phase of the study. Assuming a withdrawal rate of 10 percent, we plan to include 27 patients per treatment arm, which means 54 patients in total.

This sample size calculation only concerns the trial part of this study, no power analysis was done for the follow-up study.

Regarding the fMRI study approximately 16 of the 54 patients participating in the BonT study will be included to take part in the fMRI study. Based on a study by Thirion et al., a minimum of 16 subjects is required for fMRI studies (see also amendment 2).

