## 7.2 Randomisation, blinding and treatment allocation

Patients will be randomized using a central web-based and validated computer program (ALEA) made available by the Clinical Research Unit(CRU) in the AMC. Randomisation will be stratified by type of psychogenic jerks (in extremity vs. abdominal jerks), using variable permuted blocks.

Randomisation lists will be handed by the CRU to the AMC pharmacy, who will safeguard the code. If needed, the randomization code can be broken by the pharmacy. Neither the subject, nor the investigator is informed about allocated therapy. Serious adverse events like life-threatening side-effects, will be an indication for breaking the code for that specific subject. Non-serious adverse events will be treated, but will not be an indication for breaking the randomization code

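### The primary test ignores the factor on which randomisation is stratified; if jerk type predicts response, this costs a few points of power

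*Protocol*

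**What the plan says.** - **Randomisation (section 7.2):** "Randomisation will be stratified by type of psychogenic jerks (in extremity vs. abdominal jerks), using variable permuted blocks". No reason is given for choosing this factor.
- **Primary analysis (section 9.2, under the heading for univariate analysis):** "The difference in the proportions of patients reaching the primary outcome measure between the groups treated with BoNT and with placebo will be assessed" with the chi-square statistic or, where appropriate, Fisher's exact test. No stratum term appears.
- **Sample size (section 4.4):** the trial is sized on the same unstratified test. "A two group Chi-square test with a 0,05 two-sided significance level will have 80% power" for 0.30 against 0.70, "when the sample size in each group is 24". Then: "Assuming a withdrawal rate of 10 percent, we plan to include 27 patients per treatment arm, which means 54 patients in total".
- **Adjustment (section 9.3):** regression adjustment is foreseen only for baseline variables that turn out to differ between the arms. Section 9.1 lists jerk type among the baseline variables.

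**The concern.** Stratified blocks hold the two jerk types in balance between the arms. If jerk type predicts response, that balance removes part of the chance variation in the treatment difference. A test that pools the strata still counts the removed variation in its standard error. It then rejects too seldom, and the interval around the risk difference is wider than the design warrants.

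The conditional adjustment in section 9.3 does not close the gap. It is triggered by imbalance, so the one factor that the design balances is the one least likely to enter the model. At stake is some power and interval width in a trial of 54 patients. The correctness of a positive result is not at stake.

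**Working it through.** **1. The protocol's own figure.** Inputs from section 4.4: two-sided 0.05, 80% power, 0.30 against 0.70. With the pooled variance and no continuity correction, the mean rate is 0.50 and

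n = [1.960 × √(2 × 0.5 × 0.5) + 0.842 × √(0.3 × 0.7 + 0.7 × 0.3)]² / 0.40² = (1.386 + 0.545)² / 0.16 = 23.3, so 24 per arm.

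Allowing for withdrawal, 24 / 0.90 = 26.7, so 27 per arm and 54 in total. The odds ratio is (0.7/0.3)/(0.3/0.7) = 5.44. All of these agree with the protocol.

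**2. Why the plain test is too wide if jerk type matters.** Assume two equal strata whose response odds differ by a factor of 10, with 0.30 overall on placebo. The stratum rates are then 0.093 and 0.507.
- Variance used by the plain analysis: 0.30 × 0.70 = 0.210.
- Variance left after balancing: (0.093 × 0.907 + 0.507 × 0.493)/2 = 0.167.
- Ratio of standard errors: √(0.210/0.167) = 1.12, so the plain interval is about 12% too wide. The BoNT arm mirrors this.
- At a stratum odds ratio of 3 (rates 0.189 and 0.411), the same steps give √(0.210/0.198) = 1.03, about 3%.
- With no association the ratio is 1.

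**3. Power at the protocol's overall rates.** Simulation with 400,000 trials per setting, arms balanced within strata and overall rates held at 0.30 and 0.70. Assumed, because the protocol does not state them: extremity share 50%, 67% or 80%, and the stratum odds ratio in the first column. An exact enumeration of the same kind of settings agreed. Ranges run over the three shares.

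| Stratum odds ratio | Per arm | Plain chi-square | Mantel-Haenszel, uncorrected | Gain (points) |
|---|---|---|---|---|
| 1 | 24 | 0.836–0.837 | 0.836–0.837 | 0.0 |
| 1 | 27 | 0.839–0.840 | 0.840–0.842 | 0.1–0.2 |
| 3 | 24 | 0.840–0.843 | 0.840–0.846 | 0.1–0.3 |
| 3 | 27 | 0.845–0.846 | 0.860–0.873 | 1.5–2.7 |
| 5 | 24 | 0.844–0.850 | 0.847–0.862 | 0.3–1.2 |
| 5 | 27 | 0.851–0.854 | 0.879–0.899 | 2.8–4.6 |
| 10 | 24 | 0.851–0.862 | 0.861–0.898 | 1.0–3.6 |
| 10 | 27 | 0.861–0.866 | 0.904–0.930 | 4.3–6.4 |

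**4. Type I error** (no treatment effect, 50% response overall):

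| Stratum odds ratio | Plain, 24 per arm | Plain, 27 per arm | Mantel-Haenszel, both sizes |
|---|---|---|---|
| 1 | 5.9% | 4.2% | 4.3–5.9% |
| 3 | 5.0–5.4% | 3.5–3.7% | 4.5–5.4% |
| 5 | 4.2–4.8% | 2.7–3.4% | 4.9–5.1% |
| 10 | 2.7–4.1% | 1.7–2.9% | 4.7–5.1% |

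As the association grows, the plain test drifts down while the stratified test stays near 5%. The values slightly above 5% at weak or no association come from the discreteness of small tables, and the stratified test shares them.

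**5. The continuity correction decides whether the remedy helps.** Take 27 per arm, near-equal strata and a within-stratum odds ratio of 5.44. The continuity-corrected Mantel-Haenszel test has power 76% against 84% for the plain chi-square when placebo response is 30% in both strata. It has 74% against 80% at 20% and 40%, and 71% against 74% at 15% and 45%. The correction costs more than stratifying gains in all three.

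**The case against.** The case for leaving section 9.2 alone has real weight.

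- **The plain test is not wrong.** It is the test used for sizing, and ignoring a balanced prognostic factor does not inflate the type I error. This stands.
- **It is not always conservative.** With 30% response in both strata and 27 per arm, its type I error is about 5.4%. The claim of conservatism therefore holds only if jerk type predicts response. This stands.
- **A reader might infer that the sponsor believed jerk type to be prognostic.** The protocol gives no reason for the choice and no response figures by jerk type, so no such belief can be attributed.
- **A reader might infer that power is already marginal, or that ignoring strata could cost 12 points.** Such a figure can be produced by fixing the within-stratum odds ratio at 5.44 with placebo rates of 10% and 50%: power is then about 63% plain against 75% stratified. But that leaves the protocol's design. The BoNT rates become 0.377 and 0.845, so with equal strata the overall contrast is 0.30 against (0.377 + 0.845)/2 = 0.611. That is 31 points, not 40. Most of the shortfall from 84% to 75% and below reflects the smaller effect, and the scenario needs a stratum odds ratio of (0.5/0.5)/(0.1/0.9) = 9.
- **Section 9.3, or an analysis plan not seen here, could bring jerk type in.** Section 9.3 does so only after an imbalance that stratification should prevent. A later plan might add a stratified analysis, but the protocol itself names the plain test as primary.

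**Conclusion.** The mismatch between design and analysis is real, and its consequence is conditional and modest. If jerk type does not predict response, nothing is lost. If it does, the plain test is valid but conservative. The power forgone is 0 to 3 points at a stratum odds ratio of 3, 0 to 5 at 5, and between 1 and 7 at 10 (6.4 at most in the settings run). These figures rest on the protocol's 0.30 and 0.70 and on an assumed extremity share of 50% to 80%.

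Under those rates the plain chi-square keeps about 84% power or more, above the planned 80%. That statement concerns the chi-square branch. The Fisher branch has power 0.750 at 24 per arm and 0.763 at 27, a loss unrelated to the strata. With overall response near 50%, each cell expects about 24 × 0.5 = 12 patients, so small expected counts would not normally call for Fisher's test.

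The point is one of efficiency and coherence. It gives no ground to doubt a significant result.

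**What to change.** In section 9.2, name as the primary analysis the Mantel-Haenszel (CMH) test **without continuity correction**, stratified by jerk type as recorded at randomisation. Apply it whether or not imbalance is seen. Report the Mantel-Haenszel risk difference with its 95% confidence interval. Keep the plain chi-square as a sensitivity analysis, and leave section 9.3 for other baseline variables.

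The cost is a sentence or two, fixed before the treatment code is opened. Jerk type is already recorded for randomisation, so no data or patients are added. The sample size need not change, because in every setting in the power table the uncorrected stratified test has at least the power of the plain chi-square. The one condition is that the uncorrected statistic be stated explicitly, since the corrected form could lose more power than stratifying recovers.

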#### Intervention

BoNT or placebo (0.9% sterile saline) will be injected in muscles involved in the jerky movement. In appearance the placebo is indistinguishable from BoNT. The muscles that will be injected will be determined by a neurophysiologist experienced in treatment with BoNT according to the pattern of movements visible and according to the involved muscles measured with EMG. The number of muscles injected may differ per patient. The neurophysiologist will determine the doses to be administered. These will be similar to those used for involvement of the same muscle by other movement disorders (typically dystonia). Placebo injections consist of an equivalent volume of 0.9% sterile saline. All injections will be given by an experienced neurophysiologist, who will remain blind to the treatment allocation and will not be involved in the outcome assessments.

As dose response differs individually, patients will be treated two times. The first treatment will take place after the baseline assessment. The second treatment will take place 3 months hereafter; this is the usual time interval in the treatment of dystonia. To optimize therapy, the dose and if necessary the injection sites may be adjusted in the second session according to degree of response and occurrence of muscle weakness. After 16 weeks, the trial period ends (see also time scheme, page 14).

[figure not shown]
After the trial period, all patients will be assigned to treatment with BoNT to establish the long-term effects. In this phase of the study, patients will receive a total of 4 times injections with BoNT at 3 month intervals. This results in a follow-up period of 12 months for all patients included in the study. The length of this follow up is considered necessary because of

several reasons. First and most important, an effect of therapy may diminish over time in these patients with a chronic disorder with frequently co-occurring disease. Second, it is considered an evaluation period for certain secondary study objectives, as it may take longer than the trial period before an effect on for example, concurrent psychiatric disease is observed. Finally, this way it is possible to evaluate whether optimalization of treatment results in better response to therapy in these patients.

Additionally in 16 of 54 patients an fMRI scan will be performed before and at the end of the trial (16 weeks).

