Outcome measures 2, 5, 6, and 7 will be completed by the patients. Measure 1, 3 and 4 will be based on the video recordings and will be completed by the same independent investigator who is blind to treatment and is not involved in the injections based on the video of the patients. The psychiatric evaluations will be performed by a neuropsychologist specifically trained to perform the MINI-plus psychiatric interview.

A time schedule of the study is presented at page 14. For the trials secondary outcome measures, similar to the primary outcome measure, the difference in scores between baseline and after 16 weeks (4 weeks after the second injection) will be used. To evaluate the long term effect of treatment with BoNT the different outcome measures assessed 16 months after the start of the study (approximately 1 year after the end of the trial) will be compared with baseline (t=0) and with the assessments at the end of the trial period (t=16 weeks)

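### The month-16 versus week-16 comparison names no split by original arm; run over all patients, it would understate waning of the BoNT effect

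*Protocol*

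**What the plan says.** The trial phase is randomised: "patients will be randomized in a 1:1 ratio to treatment with BoNT or to treatment with placebo" (section 3, Study population). After week 16 both arms move into an uncontrolled follow-up, except patients with serious complications, and everyone then receives four BoNT sessions (section 5.1). For the former BoNT arm this continues treatment. For the former placebo arm it is the first exposure.

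Section 7.1.2 states that the month-16 outcomes "will be compared with baseline (t=0) and with the assessments at the end of the trial period (t=16 weeks"). Section 9.2 names the method: "For the long term effects, the assessments of individual patients at t=16 months will be compared with previous assessments using tests for paired data". It lists the paired t-test and McNemar's test, or the mean difference between month 16 and baseline. It adds mixed effects models for repeated measures but names no model terms. For the randomised phase, the same section refers explicitly to the two treatment groups. For the long-term analysis it names no group.

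On why follow-up lasts a year, section 3 (Intervention) says: "First and most important, an effect of therapy may diminish over time in these patients with a chronic disorder". A later reason there is to see whether optimising treatment improves the response.

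**The concern.** The change from week 16 to month 16 means different things in the two arms. In the former BoNT arm it shows whether the effect persists, fades or improves with adjusted treatment. In the former placebo arm it shows what happens when BoNT is started. A paired test over all patients estimates the average of the two, and the expected gain in one half offsets any loss in the other.

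This matters because only the former BoNT arm can show, between these two time points, the waning or optimisation that section 3 wants to observe. A pooled result of no change could accompany a real loss on BoNT, and a pooled gain could appear when nothing had changed on BoNT. The paired t-test on continuous outcomes averages in the same way.

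**Working it through.** **Inputs from section 4.4.** The design statement is "A two group Chi-square test with a 0,05 two-sided significance level will have 80% power", with expected responder rates of 0.30 on placebo and 0.70 on BoNT, "when the sample size in each group is 24". Then: "Assuming a withdrawal rate of 10 percent, we plan to include 27 patients per treatment arm".

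**The plan's own figure.** With pooled variance and no continuity correction:

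n = [1.96·√(2·0.5·0.5) + 0.8416·√(0.3·0.7 + 0.7·0.3)]² / 0.40² = (1.386 + 0.545)² / 0.16 ≈ 23.3, so 24 per group.

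Power at 24 is 81.2%. The odds ratio is (0.7/0.3)/(0.3/0.7) = 5.44. Inflation for withdrawal is 24/0.9 = 26.7, so 27 per arm. The sample size reproduces, and its rates are used below.

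**Pooled change.** Assume that both former arms have the same responder rate X at month 16. The protocol gives no month-16 rate, so X is an assumption, varied from 0.30 to 0.70. With 1:1 allocation:

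pooled change = ½(X − 0.70) + ½(X − 0.30) = X − 0.50

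| X at month 16 | Former BoNT arm | Former placebo arm | Pooled |
|---|---|---|---|
| 0.70 | 0 | +40 points | +20 points |
| 0.60 | −10 | +30 | +10 |
| 0.50 | −20 | +20 | 0 |
| 0.40 | −30 | +10 | −10 |
| 0.30 | −40 | 0 | −20 |

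The gap between the pooled change and the change in the former BoNT arm is (X − 0.50) − (X − 0.70) = +20 points, whatever X is. With the rounded rates of one third and two thirds that section 4.4 also mentions, the pooled change is again X − 0.50, and the gap is ½(2/3 − 1/3) = 16.7 points.

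**What the tests would show.** McNemar tests were simulated with 200,000 runs, 27 patients per arm, and an assumed within-patient correlation of 0 to 0.5. The table gives the proportion of runs with a significant result at 0.05, for the uncorrected chi-square form and, in brackets, the exact form.

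| X | Loss in former BoNT arm | Pooled test | Former BoNT arm alone |
|---|---|---|---|
| 0.60 | 10 points | 17–26% (12–19%) | 11–17% (7–8%) |
| 0.50 | 20 points | 3–4% (about 2%) | 30–54% (22–37%) |
| 0.40 | 30 points | 18–26% (12–19%) | 58–93% (49–82%) |

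At X = 0.60 almost all significant pooled results are in the direction of improvement; a significant pooled decline occurs in 0.1% of runs or fewer. With 24 rather than 27 per arm, the by-arm power for a 20-point loss is 26–50% (exact 19–30%).

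**The other listed analyses.** Both arms are free of BoNT at baseline, so month 16 versus baseline does not have this cancellation. It cannot, however, show change since week 16. If pooled, it combines patients with 2 + 4 = 6 BoNT sessions and patients with 4. A mixed model without an arm-by-time term averages the change over time across arms just as the paired test does.

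**The case against.** The protocol never says that the arms are combined. A paired test run within each arm would satisfy section 9.2, and an analysis plan that is not shown could specify that. This stands: pooling is an inference. It is nevertheless the natural reading, since all patients are carried into follow-up and the tests named are one-group tests with no arm mentioned. The protocol has fixed the time points and the tests, so this is more than a detail left for later.

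A reader might infer that waning would be hidden completely. The documents do not support that as a general claim. Exact cancellation needs an assumed month-16 rate of 50% in both arms (or rates that average 50%). Larger losses would still appear, diluted.

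A reader might also infer that the follow-up cannot answer its question. That goes too far. The follow-up objectives in section 2 speak of long-term effect, not of waning; waning appears in section 3 as a reason for the length of follow-up. Month 16 versus baseline addresses the stated objectives, and the mixed model could separate the arms if its terms were chosen to do so.

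Finally, the split does not make the study powerful. A 20-point loss would be missed in roughly half or more of the cases even in the right arm. This is correct and shapes the recommendation.

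**Conclusion.** The point holds in a limited form. As most naturally read, the month-16 versus week-16 comparison mixes maintenance with first exposure. At the protocol's expected rates it is shifted 20 points towards improvement relative to the change in the former BoNT arm: no waning appears as a gain of 20 points, a 20-point loss as no change, and a complete 40-point loss as a loss of 20. These sizes rest on the planning rates of 0.70 and 0.30, equal arm sizes and an assumed common month-16 rate. The power figures also rest on the assumed correlation of 0 to 0.5.

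The fault affects one contrast in an uncontrolled, unpowered follow-up and leaves the randomised primary comparison untouched. It should still be corrected, because that contrast is the one that speaks to the first reason given for following patients for a year.

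**What to change.** In section 9.2:

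- Report month 16 versus week 16 separately by original randomised arm. Take durability and optimisation from the former BoNT arm only; describe response after switching in the former placebo arm.
- Include arm, time and arm-by-time terms in the mixed model.
- Present the by-arm results as estimates with the 95% confidence intervals that the section already promises, and do not read a non-significant test as evidence of persistence.
- If the arms are pooled for month 16 versus baseline, state that this combines patients with six and with four BoNT sessions.

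The cost is wording only: no added visits, data or patients. Each by-arm estimate rests on about 27 patients at most, so its interval will be wider, but it will describe the intended quantity.

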## 4. STUDY POPULATION

## 4.1 Population

Patients with one or more jerks of psychogenic origin that significantly disable them in their daily functioning will be included in the study. Patients will be recruited in several manners. The patients with psychogenic jerks enrolled in an ongoing study focussing on the pathophysiology of jerky movement disorders will be evaluated for eligibility, (METC number 07/290) suitable patients from our outpatient clinic will be asked to participate and movement disorder specialists from other clinics will be asked to refer suitable patients.

Approximately 16 of the 54 patients participating in the BonT study will be included to take part in the fMRI study. These patients will be included at the UMC Groningen and will be included, irrespective of the randomised group that they're in. Furthermore 16 healthy control subjects will be included. Controls need to be healthy, both neurological and psychiatric, and are age- and gender- matched with the participants with psychogenic movement disorder. Controls on medication that affect the brain (like benzodiazepines/opiates/barbiturates) or with a history of substance abuse are excluded from this study.

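### The main fMRI outcome is defined as BOLD change before versus after BoNT, but patients are scanned from both arms, so only about 8 of the 16 can supply that contrast

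*Protocol*

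**What the plan says.** **Outcome.** Section 9.2 of the protocol, in its separate fMRI paragraph, states that "the main study outcome measure is the difference in BOLD signal between scans of patients with psychogenic jerks before and after treatment with BoNT". It names no test and no comparison between arms. The comparison with healthy volunteers is listed as secondary.

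**Who is scanned.** Section 4.1: "Approximately 16 of the 54 patients participating in the BonT study will be included to take part in the fMRI study", and they enter "irrespective of the randomised group that they're in". Section 3 (Study population): "patients will be randomized in a 1:1 ratio to treatment with BoNT or to treatment with placebo".

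**When.** Section 3 (Intervention) and the visit scheme in section 7.3.4 place the scans at baseline and at 16 weeks, the end of the placebo-controlled phase. The 16-month visit lists no scan. Open treatment starts later: "After the trial period, all patients will be assigned to treatment with BoNT to establish the long-term effects".

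**How many.** Section 4.4 supports the number with a cited methodological study, from which it concludes that "a minimum of 16 subjects is required for fMRI studies". It also refers to amendment 2. It gives no effect size, variance, significance level or power for the fMRI outcome.

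**Related text.** Section 2 lists a difference in brain function on fMRI among the secondary objectives of the randomised trial. Section 7.1.2 lists fMRI change as item 11 and says that secondary trial outcomes use the change from baseline to 16 weeks.

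**The concern.** A patient randomised to placebo has one scan before placebo and one after placebo, and never a scan after BoNT. The outcome defined in section 9.2 therefore cannot be observed in about half of the patients scanned to measure it.

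This leaves two ways to apply the sentence as written, and both are unsatisfactory. Restricted to the BoNT arm, it rests on about 8 patients and ignores the control group. Applied to all 16, it averages over BoNT and placebo and no longer measures a BoNT effect. In the pooled form, a placebo response, or a change that comes simply from being scanned a second time, cannot be told apart from a drug effect. Section 4.4 itself warns that placebo effects may be large in psychogenic disorders and expects about one third of placebo patients to reach the clinical endpoint.

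The interpretation of the sub-study is at stake. Section 10.4 expects the scans to inform on the effectiveness of BoNT.

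**Working it through.** **1. The plan's own figures.** Section 4.4: 24 per group and 10% withdrawal give 24 / 0.9 = 26.7, rounded up to 27 per arm and 54 in total. This reproduces. The fMRI number of 16 cannot be reproduced, because it comes from a citation without an effect size, SD, significance level or power.

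**2. BoNT patients among those scanned.** Inputs: 54 patients, 27 on BoNT, 16 scanned without regard to arm. Treated as a random draw (hypergeometric):
- mean = 16 × 27/54 = 8
- variance = 16 × 0.5 × 0.5 × (54 − 16)/(54 − 1) = 2.87, so SD = 1.69
- 2.5% to 97.5% range: 5 to 11
- chance that all 16 are on BoNT: about 6 in 10 million

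A binomial model (16, 0.5) gives the same mean, a range of 4 to 12, and 0.5^16 = 1.5 in 100,000. Section 7.2 stratifies randomisation by jerk type only, and the fMRI patients come from one hospital, so an even split is expected but not assured.

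**3. After-BoNT scans in placebo patients.** Scans are at week 0 and week 16, BoNT for placebo patients starts after week 16, and no scan is listed at 16 months. The number is 0.

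**4. What each contrast could detect.** The protocol gives no fMRI effect size, so *d* is an assumption: the mean change on BoNT in SDs of within-patient change, with no change on placebo. The table assumes a single scalar outcome and a two-sided t-test at 0.05, which the protocol does not specify for BOLD. The noncentrality is *d*√n for paired data and *d*√(8/2) = 2*d* for 8 versus 8. The pooled row was simulated with 8 patients at *d* and 8 at 0.

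| Contrast | d = 0.5 | 0.8 | 1.0 | 1.5 |
|---|---|---|---|---|
| Paired, 16 BoNT patients (not available) | 46% | 85% | 96% | >99% |
| Paired, 8 BoNT patients | 23% | 50% | 68% | 95% |
| Between arms, 8 vs 8 | 15% | 32% | 46% | 80% |
| Pooled before-after, all 16 | 14% | 27% | 37% | 62% |

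**5. Pooled contrast when BoNT adds nothing.** If both arms change by the same *d*, the pooled test behaves like the first row: it is significant in 46% of cases at 0.5 SD and 85% at 0.8 SD. The between-arm test stays at 5%. Whether any such common change occurs is not known from the protocol.

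**The case against.** Three objections carry weight.

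*The minimum of 16 is met.* A reader might infer from the 8 expected BoNT patients that the sub-study falls short of its own minimum. Section 4.4 does not support that. It asks for 16 subjects and plans about 16, without saying that the figure applies per arm, per contrast or to treated patients only. The cited study and amendment 2 are not available to settle it. This objection stands. What remains is narrower: the count covers both arms, and the protocol does not show that it suits the outcome in section 9.2.

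*A between-arm comparison may already be intended.* Section 2 places fMRI among the randomised trial's objectives, section 7.1.2 makes it a secondary outcome based on change to 16 weeks, and section 9.2 gives a t-test or ANCOVA for continuous secondary outcomes. The Summary speaks more neutrally of scans before and after the treatment intervention. On that reading the fMRI sentence is loose wording for a change score. A reader might also infer that the plan will credit placebo change to BoNT; that follows only if the sentence is applied as a single-group test. The objection stands in part. The fMRI paragraph is separate, it is the only place that names a main fMRI outcome, and it names BoNT rather than trial treatment and no arm contrast.

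*The sub-study is small and secondary.* This is correct. It limits the severity but leaves the contradiction in place.

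**Conclusion.** The main fMRI outcome in section 9.2 is wrong as written: the enrolment rule and scan schedule allow it to be observed in about 8 of 16 patients (95% range 5 to 11), and in no placebo patient. This rests only on the 1:1 allocation, on entry without regard to arm and on the scan times, all stated in the protocol. A pooled before-after contrast could not be attributed to BoNT.

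The power figures are illustrations over assumed effects of 0.5 to 1.5 SD. They show that 8 versus 8 is informative only for large effects, and they do not predict the result.

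This should be fixed, but it concerns the sub-study only. The CGI-I primary endpoint, the sample size of 54 and the blinding are untouched.

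**What to change.** - **Section 9.2:** define the main fMRI outcome as the between-arm difference (BoNT minus placebo) in BOLD change from baseline to week 16, and label it exploratory. This agrees with section 2 and with section 7.1.2, item 11.
- **Section 4.4:** state that about 8 patients per arm are expected, and that 16 refers to all scanned patients rather than to BoNT-treated patients.

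Both changes are to wording and need no extra scans or patients. They should be made before unblinding, so that the contrast is not chosen with the results in view. The cost is a more modest claim for the sub-study: illustrative power of 15% to 80% for 8 versus 8 over the assumed range, and somewhat less if the arms turn out uneven.
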